8.2 Definition of study populations

Full analysis set (FAS): All patients enrolled in the study.

Per protocol (PP) analysis set: All patients enrolled in the study who completed the study without any major protocol violations.

8.3 Overall statistical and analytical plan

8.3.1 General statistical issues

A detailed Statistical Analysis Plan (SAP) describing further details of the statistical analyses to be used will be prepared prior to first patient in.

All continuous variables will be summarized with descriptive statistics including number of observations, mean, standard deviation, median, quartiles, minimum and maximum values. Categorical variables will be summarized in frequency tables including number of observed responses in each category as well as percentages. Number of missing observations will also be displayed. No formal statistical hypothesis testing is planned.

Baseline is defined as the measurements taken on Visit 1.

Historical data (6-months before enrolment) will be tabulated by type of haemophilia, total and listed.

8.3.2 Demographics and baseline characteristics

All demographics and baseline characteristics will be summarized with descriptive statistics by type of haemophilia and in total. Individual patient data will be listed.

Disposition: Patient disposition will be listed with any withdrawals flagged. Frequencies (number and %) of the total number of patients enrolled, completed, prematurely withdrawn (including reason for withdrawal) from the study, number of sites with at least one patient enrolled, number of patients in the FAS and number of patients in the PP set will be summarized.

Demographics: Demographic data (age, weight, height, severity of haemophilia and type of haemophilia (A or B)) at baseline visit will be summarized and listed by descriptive statistics.

Number and location of impaired joints at baseline will be presented by descriptive statistics.

8.3.3 Analysis related to primary objective

The primary objective is to evaluate the overall joint status as detected by US in haemophilia A and B patients treated with rFVIIIFc or rFIXFc prophylaxis over the 18-month study period.

The primary endpoint is change from baseline in total HEAD-US score up to month 18 (EOS) and will be based on both the FAS and PP set.

The primary endpoint, change from baseline, will be calculated from baseline (Visit 1) to month 18 (EOS). The change in HEAD-US score will also be calculated from baseline to month 6 and month 12. Mean change from baseline for the primary endpoint, will be estimated using a generalized linear mixed model for repeated measures, adjusted for clinically important covariates (for example, age, severity of haemophilia, type of haemophilia, presence of joint disease at inclusion, prophylactic regimen and dose intensity) as applicable. The estimated mean

Sobi

Eftrenonacog alfa/Alprolix® - Efmorocog alfa/Elocta®

Clinical Study No: Sobi.HAEM89-007

change from baseline in Total HEAD-US score will be presented with 95% confidence interval. In general, patients with events that could affect the interpretation of the Total HEAD-US score but not leading to discontinuation of treatment will be included in the primary analysis. Patients with events leading to discontinuation of treatment will be included in the primary analysis including all data collected up to discontinuation. To assess the robustness of these results, sensitivity analyses will be performed including one based on the PP analysis set. Further details will be specified in the SAP.

Examples of subgroups that will be created if applicable, to further explore the endpoint are age (6-<12, 12-<18, \geq 18 years), severity of haemophilia (mild/moderate/severe), type of haemophilia (A/B), presence of joint disease at inclusion (synovial hypertrophy and/or osteochondral changes), prophylactic regimen (primary/secondary/tertiary), dose intensity cross tabulated by change vs. no change in HEAD-US score, treatment (on demand vs. prophylaxis) prior to enrolment into the study and compliance (if e.g. 20% of the patients have < 80% compliance).

If there are few mild and moderate patients then these two severities will be pooled.

The HEAD-US score represents the sum of item scores for abnormalities detected. Its values range from 0 (minimum) to 8 (maximum), see Table 4.

Table 4 **HEAD-US scoring method**

Disease activity (synovitis)	Scale
Hypertrophic synovium	
Absent/Minimal	0
Mild/Moderate	1
Severe	2
Disease damage (articular surfaces)	
Normal	0
Echotexture abnormalities, focal partial/full-thickness loss of the articular cartilage involving <25% of the target surface	1
Partial/full-thickness loss of the articular cartilage involving at least \leq 50% of the target surface*	2
Partial/full-thickness loss of the articular cartilage involving >50% of the target surface	3
Complete cartilage destruction or absent visualization of the articular cartilage on the target bony surface	4
Bone	
Normal	0
Mild irregularities of the subchondral bone with/without initial osteophytes around the joint	1
Deranged subcondral bone with/without erosions and presence of prominent osteophytes around the joint	2
Note: Elbow: anterior aspect of the distal humeral epiphysis, Knee: femoral trochlea; Ankle: anterior aspect of the talar dome.	

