Extended half-life products used for replacement factor therapy have been developed utilizing Fc or albumin fusion technology, or pegylation, to prolong their half-life (13). Efmoroctocog alfa [a recombinant FVIII Fc fusion protein, Elocta®] (rFVIIIFc) and Eftrenonacog alfa [a recombinant FIX Fc fusion protein, Alprolix®] (rFIXFc) are recombinant coagulation factor concentrates with extended half-life. In contrast to standard half-life factor replacement products, the addition of the Fc region of human immunoglobulin G1 (IgG1) to the recombinant factor allows rFVIIIFc and rFIXFc to bypass lysosomal degradation and remain circulating in the bloodstream longer than standard half-life factor replacement products, thus prolonging the plasma terminal half-life. rFVIIIFc first received market authorization in June 2014 in the US, for the treatment of haemophilia A. Thereafter, in November 2015, it received market authorization in the European Union (EU) under the tradename Elocta®. rFIXFc first received market authorization in the US March 2014 and then in Europe in May 2016 for the treatment of haemophilia B under the tradename Alprolix®.

Despite the use of prophylaxis many patients still experience joint bleeds which may lead to joint deterioration over time (14, 15). Furthermore, not all bleeds may be clinically evident, as there are indications of subclinical bleeds in patients receiving treatment for their haemophilia (16). It is therefore important to gather additional information on the joint health of haemophilia patients using currently available examination methods.

Thorough examination of the joints and follow-up of patients is a crucial part of patient management and helps to identify when there is a need to adjust the treatment regimen. There are currently several examination methods to identify joint damage early on, including clinical joint examination and different imaging techniques. The functional Hemophilia Joint Health Score (HJHS) (17, 18, 19) for clinical joint assessment and more recently the Haemophilia Early Arthropathy Detection with UltraSound (HEAD-US) protocol for joint imaging are two established examinations.

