6.3.3 Withdrawal of patients from study

6.3.3.1 Withdrawal from study

Whenever possible and irrespective of the reason for withdrawal, the patient should be examined as soon as possible. All relevant assessments should be completed, preferably according to the schedule of events (see section 6.5.1.1). The Case report form (CRF) should be completed as far as possible. Date and reason for the study withdrawal should be clearly described in the CRF.

A patient should be withdrawn from the study for any one of the following reasons:

- The patient develops factor VIII or FIX inhibitory antibodies (inhibitor titre ≥ 0.60 BU/mL)
- The patient or his legally authorized representative(s) withdraws consent
- The patient enrolls into an interventional clinical study in which an investigational treatment or approved therapy for investigational use is administered
- The patient enrolls into a low-interventional clinical study where the assessments performed are of such nature that the patient cannot be considered treated per usual routine practice
- The patient discontinues prophylactic treatment with rFVIIIFc or rFIXFc
- The patient is no longer willing to undergo the mandatory US examination

If any Adverse Event (AE) is associated with the withdrawal this should be recorded in the CRF.

If the patient withdraws consent for disclosure of future information (data, samples), the sponsor may retain and continue to use any data collected before such a withdrawal of consent.

Patients will not be withdrawn if they miss a study visit.

If a patient withdraws from the study and more than 3 months since the last study visit have passed, all assessments should be performed to the extent possible. If a patient withdraws from the study less than 3 months since the last visit, PRO collection and HJHS assessment should be performed to the extent possible.

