6.3.4 Replacement of withdrawn patients

Withdrawn patients will not be replaced.

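### Does a completers-only per-protocol set leave the primary HEAD-US result without a usable check against selective dropout?

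*Combined protocol and SAP*

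**What the plan says.** Section 8.3.3 states that the primary endpoint, change from baseline in total HEAD-US score to month 18, "will be based on both the FAS and PP set". The estimator is a mixed model for repeated measures with a 95% confidence interval. Patients whose treatment stops "will be included in the primary analysis including all data collected up to discontinuation". On robustness: "To assess the robustness of these results, sensitivity analyses will be performed including one based on the PP analysis set". The section then refers to the SAP for further detail, and section 8.3.8 leaves the handling of missing data to the SAP as well.

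Section 8.2 defines FAS as everyone enrolled and PP as: "All patients enrolled in the study who completed the study without any major protocol violations".

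Reasons for withdrawal in section 6.3.3.1 include an inhibitor, "The patient discontinues prophylactic treatment with rFVIIIFc or rFIXFc" and "The patient is no longer willing to undergo the mandatory US examination". Section 6.3.4 adds: "Withdrawn patients will not be replaced". Section 6.3.3.1 also says that a missed visit is not a reason for withdrawal. It asks for every assessment, where feasible, if a patient leaves more than 3 months after the last visit. For an exit sooner than that it names only the PROs and HJHS. Section 6.5.1.5 repeats this rule.

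**The concern.** The one sensitivity analysis that the protocol names uses less information about leavers than the analysis it is meant to test. A patient who stops prophylaxis after month 12 contributes scans to the FAS model and nothing to PP. Neither analysis uses any outcome after withdrawal. If patients with worsening joints leave more often, both estimates could lie too low, and their agreement could be read as reassurance.

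There is a conceivable route to such loss. Section 4.1 says joint examination "helps to identify when there is a need to adjust the treatment regimen", and a patient who stops the study product must be withdrawn. The bias would run towards stable or improved joints, which is the outcome that section 4.1 expects. A FAS-PP difference would not be easy to interpret either, because PP removes early leavers and major violators together.

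**Working it through.** **1. The plan's own precision.** Half width = 1.96 × SD / √n (section 8.1, Table 3).
- SD 13, n 250: 1.96 × 13 / 15.81 = 1.61 (stated 1.61)
- SD 7, n 250: 0.87 (stated 0.87)
- SD 10, n 250: 1.24, or 1.25 with the t quantile (stated 1.25)
- SD 13, n 200: 1.80 (stated 1.80)

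The table reproduces. Biases below can be compared with 1.61 and with the clinically meaningful worsening of 2 in section 8.1.

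**2. Set-up of the illustration.** From the protocol: scans at months 6, 12 and 18, and SD 13 for the month-18 change. Assumed, because the documents do not give them:
- true mean change 0 at each visit
- SD at months 6 and 12 equal to 0.6 and 0.8 of the month-18 SD
- correlation 0.7 between adjacent visits
- dropout after months 6 and 12, logistic with slope 1.0 per SD
- total loss of 20% or 10%

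The PP estimate is the mean of completers, with no violations. The FAS estimate is maximum likelihood on all data up to leaving. Each setting has 1,000,000 simulated patients. A negative value means false improvement.

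**3. Leaving after worsening already seen on a scan.**

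| Lost | FAS | Completers |
|---|---|---|
| 20% | about 0 | -1.42 |
| 10% | about 0 | -0.72 |

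The primary analysis is right and PP is not. At 20% lost they differ by about 1.4.

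**4. Leaving on worsening not yet scanned, with the withdrawal-assessment rule.** A withdrawal scan is assumed to capture the value that the next visit would have shown.

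| Lost | Leavers scanned at withdrawal | FAS |
|---|---|---|
| 20% | none | about -1.1 |
| 20% | half | about -0.5 |
| 20% | all | about 0 |
| 10% | none | about -0.6 |
| 10% | half | about -0.3 |
| 10% | all | about 0 |

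At 20% lost the completers' mean stays near -2.07 in all three rows. The FAS-PP gap is therefore about 2.07 - 1.1 = 1.0 with no withdrawal scans, 2.07 - 0.5 = 1.6 with half, and 2.1 with all. The more of these scans are made, the more clearly the two sets separate.

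**5. When the two sets agree and are both wrong.** This happens if leaving is unrelated to anything scanned and leavers worsen by D points afterwards. Both estimates then miss the all-enrolled mean by share lost × D: 0.10 × 5 = 0.5; 0.20 × 5 = 1.0; 0.20 × 10 = 2.0. It also happens if every leaver goes before month 6 according to an unseen month-18 change and none is scanned: both estimates are -2.25 at 20% lost and -1.18 at 10%. Under section 6.3.3.1, only exits within about 3 months of baseline fall outside the all-assessments rule in that second case.

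**6. What a new PP definition would do.** If PP kept each patient's data up to withdrawal or first major deviation, then with no deviations it would equal FAS. The gaps in steps 3 and 4 would become 0, and the FAS estimate would not move.

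**The case for a change.** The case for a change is that the protocol gives PP a robustness role and fixes a definition that cannot fill it for dropout, whatever the SAP adds. Section 8.3.4 carries the same two sets to all secondary endpoints. No hypothesis test is planned, so the estimate and its interval are the product of the study and bias in them is the error that matters. The withdrawal rule has holes. Patients leaving within 3 months of a visit are asked only for PROs and HJHS, ultrasound refusers will not be scanned, uptake is only as far as feasible, and the wording that keeps data up to discontinuation could be read to exclude a scan made after the product was stopped.

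Part of this stands. FAS-PP agreement is not evidence against dropout bias, a difference mixes two causes, and those groups carry a residual risk.

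The rest is weaker. Section 8.3.3 offers PP as one of several sensitivity analyses and does not claim that it tests dropout. The route from worsening to exit is thin: section 6.5.9 records changes of dose, frequency or other management at each visit, those patients stay in the study, and no withdrawal reason refers to ultrasound worsening. Completion is an ordinary condition for a PP set. The alternative of cutting data at the first major deviation can itself be selective. A delta-adjusted analysis would be reasonable, but it belongs to the missing-data methods that section 8.3.8 assigns to the SAP, which is not in the document reviewed. It would also have to say whether delta stands for an on-treatment or an off-treatment value.

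**Conclusion.** The observation is correct, and the plan can stay as it is. The primary FAS model already does what matters. It is about unbiased if leaving follows scanned worsening, and withdrawal scans reduce its bias if leaving follows unscanned worsening (SD 13, 20% lost: about -1.1, -0.5 and 0 with none, half and all of leavers scanned). In those settings a completers-only PP departs from FAS and so flags selective loss. Redefining it would give up that signal without changing the primary result. Section 8.3.2 reports withdrawals with reasons and the size of both sets, so a reader can see how much loss there was.

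The sizes rest on assumed dropout rate, strength, correlation and scan uptake. At 10% lost, the FAS bias of at most about 0.6 in the step 4 settings is well below the planned half width of 1.61. If all leavers went unscanned before month 6, it could reach 1.18. The point for whoever reports the study is one of interpretation: FAS-PP agreement should not be presented as evidence against dropout bias. The natural reading, that withdrawal scans enter the FAS model, can be confirmed in the SAP.

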Favourable joint outcomes are expected with modern haemophilia A and haemophilia B management. However, evaluation of long-term treatment outcomes is hampered by the delay between bleeding episodes during childhood and resulting joint outcomes in adulthood. Future research with combined US and/or Magnetic resonance imaging (MRI) is needed to better understand joint outcomes. Ultrasound paired with physical examination increases the sensitivity for detection of joint damage (23). Accordingly, the expected joint health outcomes, based on HEAD-US scoring, in patients receiving adequate prophylactic treatment is at least the maintenance of a stable joint status or the improvement in reversible lesions for the patients with already established joint damage.

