8.1 Determination of sample size

With a sample size of 250 patients (200 with haemophilia A and 50 with haemophilia B) assuming a standard deviation of 13, the mean change from baseline in Total HEAD-US score will be estimated with a level of accuracy that is lower than a clinically meaningful worsening of 2, e.g. a half width of 1.61 (Table 3). The standard deviation is based on the expected variability among the patients with regards to prior treatment before enrolment and the diversity of joint status.

Table 3 **Determination of sample size**

Confidence level	Standard deviation	n	Half width
95%	7	250	0.87
95%	10	250	1.25
95%	13	250	1.61
95%	13	200	1.80

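### The one grouping of patients by HEAD-US outcome has no direction, so it cannot show whether dose intensity goes with better or worse joints

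*Combined protocol and SAP*

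**What the plan says.** Section 8.3.3 estimates the primary endpoint, change in total HEAD-US score to month 18, as a mean from a mixed model. The estimated "change from baseline in Total HEAD-US score will be presented with 95% confidence interval". Dose intensity is named there as a possible covariate.

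The same section then gives an open, conditional list: "Examples of subgroups that will be created if applicable, to further explore the endpoint are age", followed by severity, type of haemophilia, joint disease at inclusion and others. One entry is "dose intensity cross tabulated by change vs. no change in HEAD-US score". It defines neither the direction nor the size of a change. The other entries group patients by baseline, treatment or compliance features, not by HEAD-US outcome.

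Section 8.1 mentions a "clinically meaningful worsening of 2", but only to judge the precision of the mean. Nothing in Section 8.3 uses that figure again.

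Section 4.1 states the expected result with a direction: "at least the maintenance of a stable joint status or the improvement in reversible lesions". Section 6.2 justifies 18 months of follow-up partly as long enough to show that joint status has stabilised.

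Section 8.3.1 requires the SD, median, quartiles, minimum and maximum for every continuous variable. It defers further detail to a separate SAP, which is not part of the supplied document.

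**The concern.** The study asks whether joints stay stable or improve on prophylaxis. Readers will want to know how many patients worsened, how many held steady and how many improved. Section 8.3.4 plans counts of this kind for joint bleeds (0, 1, 2 and so on) and for target joints, but the HEAD-US score has no such count.

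The one table that does classify patients by HEAD-US outcome pools the two directions. If higher dose intensity went with improvement, or with worsening, the table could look the same. It would then be open to misreading on a question that matters to clinicians, namely whether treatment intensity tracks joint outcome.

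**Working it through.** **1. The plan's own figure.** The inputs from Section 8.1 are SD 13, n = 250 and 95% confidence. Half width = 1.96 × 13 / √250 = 1.611, against 1.61 stated. The other rows of Table 3 also reproduce within 1%: 0.868 (stated 0.87), 1.240 with the normal quantile or 1.246 with the t quantile (stated 1.25), and 1.802 (stated 1.80). This confirms how Section 8.1 uses the 2 points: "lower than a clinically meaningful worsening of 2, e.g. a half width of 1.61". It is a yardstick for the interval around the mean.

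**2. Loss of direction, with no distributional assumption.** Let D be a patient's change. A changed/unchanged split depends only on the size of D, whatever cut-off is chosen. A cohort with changes D and its mirror image with changes −D therefore give exactly the same table. No dose-intensity comparison built on the split can tell the two apart.

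**3. Illustration.** Assumptions: change is normal with mean m and standard deviation SD, rounded to whole points, and any non-zero change counts as changed. SDs of 7, 10 and 13 are those in Table 3. SD 3 and the means of ±2 are assumed for illustration.

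- Changed = 1 − [Φ((0.5 − m)/SD) − Φ((−0.5 − m)/SD)]
- Worsened by ≥2 = 1 − Φ((1.5 − m)/SD)

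For SD 13 and m = +2:

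- Changed = 1 − [Φ(−0.115) − Φ(−0.192)] = 0.970
- Worsened by ≥2 = 1 − Φ(−0.038) = 0.515

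For SD 13 and m = −2:

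- Changed = 0.970 again
- Worsened by ≥2 = 1 − Φ(0.269) = 0.394

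| SD | Changed, mean +2 | Changed, mean −2 | Worsened ≥2, mean +2 | Worsened ≥2, mean −2 |
|---|---|---|---|---|
| 13 | 97.0% | 97.0% | 51.5% | 39.4% |
| 10 | 96.1% | 96.1% | 52.0% | 36.3% |
| 7 | 94.5% | 94.5% | 52.8% | 30.9% |
| 3 | 89.4% | 89.4% | 56.6% | 12.2% |

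The changed column is identical for opposite outcomes. A directional column separates them.

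**4. Is a three-way split estimable at the planned size?** Half width = 1.96 × √(p(1 − p)/n).

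| n | p = 10% | p = 50% |
|---|---|---|
| 250 | 3.7 points | 6.2 points |
| 200 | 4.2 points | 6.9 points |
| 50 | 8.3 points | 13.9 points |

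The planned enrolment ("With a sample size of 250 patients (200 with haemophilia A and 50 with haemophilia B") is adequate overall and for haemophilia A. It is coarse for haemophilia B. Missing month-18 scores widen all of these intervals.

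**The case against.** The strongest reply is that direction is not lost from the plan as a whole, and that is correct. The primary model analyses signed change and may include dose intensity as a covariate. The synopsis lists intensity of treatment among the subgroups for exploring the endpoints. Quartiles, minimum and maximum of change would expose improvers and worseners cancelling in the mean: with mean 0 and a normal SD of 13, the quartiles would be about ±0.674 × 13 = ±8.8. The cross-tabulation is also only an example, conditional and exploratory, in a study that plans no hypothesis test. The separate SAP could still define better categories.

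What remains is narrower. The table as worded cannot answer a directional question, and quartiles do not give the proportion who worsened, stayed stable or improved.

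A reader might go further in three ways that the documents do not support:

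- **That the plan ignores its own patient-level threshold.** Section 8.1 applies the 2 points to the precision of the mean and never presents them as a within-patient cut-off.
- **That a one-point difference counts as change.** The plan leaves change undefined, and it gives no repeat-scan error from which to judge how often a stable patient would be misclassified.
- **That some 45% of patients would worsen by 2 or more even with a mean change of 0.** This follows from "assuming a standard deviation of 13" and a normal shape: 1 − Φ(1.5/13) = 0.454. Section 8.1 bases that SD on variation in prior treatment and joint status, and a normal change of that spread is doubtful on a 0 to 48 scale. It is not a forecast.

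**Conclusion.** The point holds in a limited form. In the supplied text, the only grouping of patients by HEAD-US outcome pools improvement with worsening, so it cannot show which way dose intensity and joint outcome go together. No analysis reports the proportions worsened, stable and improved, although the protocol's stated expectation is stability or improvement.

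The loss of direction follows from the wording and needs no assumption about distribution, SD or reading error. The percentages in the working depend on assumed normality and assumed means, and serve only to illustrate.

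This does not show an error in the primary analysis. The mean change, its interval, the covariate adjustment and the planned descriptive statistics are all unaffected. It is a cheap improvement to an exploratory analysis, and the finding that no such proportions are planned applies only to the supplied document.

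**What to change.** In Section 8.3.3, or in the SAP:

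- Replace the changed/unchanged split with worsened / stable / improved in total HEAD-US score from baseline to month 18.
- Use these categories in the dose-intensity cross-tabulation.
- Report n (%) with 95% CI overall for FAS patients with a month-18 score, and show the number missing. The FAS is all enrolled patients and withdrawn patients are not replaced, so the denominator must be explicit. State how scans taken at early withdrawal are handled.
- Use 2 points as the cut-off (stable then means a change of −1, 0 or +1) with a sentence justifying its within-patient use. Alternatively, show any worsening and any improvement alongside it.

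The cost is one derived variable, one table and a cut-off that has to be defended. No extra data are collected and the sample size does not change. The remaining weakness is that proportions among patients with a month-18 score may mislead if those who leave differ in joint outcome, which is why the missing count belongs in the same table.
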